**Table 4-1 Subject classification rules**

Analysis set	PD codes that cause a subject to be excluded	Non-PD criteria that cause a subject to be excluded
Safety set	None	No treatment taken
PD analysis set	None	No treatment taken, no valid PD data

If updates to this table are needed, an amendment to the SAP needs to be implemented prior to DBL.

Comercially Confidential Information

Commercially Confidential Information

## **6 Statistical methods for Pharmacodynamic (PD) parameters**

### **6.1 Primary objective**

The primary objective of this study is to assess efficacy of CMK389 in participants with moderate to severe AD. This analysis will be performed on the safety analysis set.

#### **6.1.1 Variables**

The primary variable is the IGA response at Week 16, defined as clear or almost clear at Week 16 with at least 2-point reduction from baseline.

The IGA rating scale is a Validated Investigator Global Assessment scale for Atopic Dermatitis (vIGA-ADTM) and it describes the overall disease severity for the whole body on a 5-point scale: clear (0), almost clear (1), mild (2), moderate (3), and severe (4).

For the descriptive analysis ([Section 6.1.2](#)) the placebo groups (i.e. placebo i.v. and placebo s.c.) will be presented both separately and pooled. For the inferential analysis ([Section 6.1.3](#)), the two placebo groups (placebo s.c. and i.v.) will be only presented pooled.

Baseline is considered to be the last assessment (including those from unscheduled visits) obtained before the first dose of study treatment.

The primary clinical question of interest is: What is the effect of CMK389 versus placebo on IGA response after 16 weeks of treatment in patients with moderate or severe atopic dermatitis without any relevant use of prohibited medication or use of rescue medication taken after first 6 weeks.

Prohibited or rescue medication are relevant when their use may have a potential confounding effect on the efficacy assessment.

This estimand will enable assessment of the effect of CMK389 for the full duration in the absence of relevant use of prohibited medication or use of rescue medication taken after the first 6 weeks.

The primary estimand is described by the following attributes:

**Population:** Adult participants with moderate to severe atopic dermatitis is the target population for biologics (Beck et al 2014, Simpson et al 2016) and is defined by an IGA score of moderate to severe (3 or 4) and an EASI score of at least 12 as defined by the study inclusion and exclusion criteria who were randomized to treatment. Further details about the population are provided in Section 5 of the protocol. This implies that analyses will be based on the safety analysis set.

**Endpoint:** IGA response at week 16, where IGA response is defined as clear or almost clear and with at least a 2-point reduction compared to baseline and no use of confounding therapy before the assessment time point.

**Treatment of interest:** the treatment (the investigational treatment CMK389 or placebo) actually taken for the entire study duration without any use of prohibited medications or use of rescue medication taken after the first 6 weeks.

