**Handling of remaining intercurrent events:**

1. Relevant use of rescue therapy (after first 6 weeks of treatment)
2. Relevant use of prohibited medication to treat AD symptoms or with impact on efficacy
3. Study treatment discontinuation due to lack of efficacy
4. Study treatment discontinuation due to AE related to AD, e.g. worsening of AD
5. Study treatment discontinuation due to AE not related to AD or due to lack of tolerability
6. Study treatment discontinuation due to other reasons (e.g. administrative if participant relocates to a region where the trial is not offered, or withdrawal of informed consent)

For the intercurrent events 1 to 4, a composite strategy will be used: use of any therapy (prohibited or rescue medication taken after the first 6 weeks) as well as any study treatment discontinuation due to lack of efficacy or due to AE related to AD are considered as unfavorable outcome, i.e. the participant will be treated as a non-responder.

For the intercurrent events 5 to 6, a treatment policy strategy will be used and the intercurrent event will be ignored (set data after discontinuation to be missing)

**The summary measure:** treatment difference of the CMK389 and placebo in absolute responder rates.

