#### **6.1.3.1 Handling of remaining intercurrent events of primary estimand**

Relevant use of any therapy (prohibited or rescue medication taken after the first 6 weeks) as well as any study treatment discontinuation due to lack of efficacy or due to an adverse event (AE) related to AD are considered as unfavorable outcomes. In that case, the composite strategy will be followed, i.e. the participants will be treated as non-responders.

The data on relevant use of rescue or prohibited medication taken after the first 6 weeks was provided by TME under blinded medical review,

Commercially Confidential Information

Study treatment discontinuation due to other reasons and AEs not related to AD or due to lack of tolerability will be handled with a treatment policy strategy, i.e. they will be ignored (no carry-forward data will be needed).

Frequency of patients with intercurrent events will be summarized by treatment arm. A patient may experience the same intercurrent event more than once during the trial and will be counted only one time for that intercurrent event.

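### Does the extra therapy clause in the SAP's Endpoint attribute create a second responder rule for rescue used in the first 6 weeks?

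*SAP*

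**What the plan says.** SAP 6.1.1 describes the primary variable twice. The opening sentence has the IGA criteria only: "defined as clear or almost clear at Week 16 with at least 2-point reduction from baseline". The Endpoint attribute repeats them and adds "no use of confounding therapy before the assessment time point". The protocol's primary variable (Section 2.1) has no such addition.

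The same SAP section says when medication matters: "Prohibited or rescue medication are relevant when their use may have a potential confounding effect on the efficacy assessment". Its treatment of interest is treatment taken "without any use of prohibited medications or use of rescue medication taken after the first 6 weeks". Intercurrent event 1 begins "Relevant use of rescue therapy (after first 6 weeks of treatment", and event 2 is "Relevant use of prohibited medication to treat AD symptoms or with impact on efficacy". Events 1 to 4 are handled by a composite strategy, so the participant becomes a non-responder.

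SAP 6.1.3.1 turns this into a scoring rule, which begins "Relevant use of any therapy (prohibited or rescue medication taken after the first 6 weeks", and names its data source: "The data on relevant use of rescue or prohibited medication taken after the first 6 weeks was provided by TME under blinded medical review". The text directly after that sentence is blacked out in the public version.

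Protocol 6.2.3 foresees topical rescue before Week 12. The footnote to protocol Table 6-2 says that rescue used under that section is not prohibited medication.

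**The concern.** The added clause ends at the assessment but has no start, so on its face it reaches back into the first 6 weeks. Rescue in that period is foreseeable, and the Table 6-2 footnote keeps it out of event 2. Take a participant who had topical rescue in Week 4, judged confounding, and who meets the IGA criteria at Week 16. The Endpoint attribute read alone makes this participant a non-responder. The opening definition, event 1 and SAP 6.1.3.1 make the same participant a responder.

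This is the only primary variable and the groups are small, with about one responder expected on pooled placebo. If two programmers could derive different flags, the observed difference would depend on which sentence each had read.

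A side question concerns prohibited medication. The parenthesis in the scoring rule, and more so the data-source sentence, can be read as applying the Week 6 limit to prohibited medication as well as to rescue, although event 2 has no time limit.

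**Working it through.** **Which texts set a start for rescue**

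| Place | Disqualifying rescue |
|---|---|
| SAP 6.1.1, opening definition | no therapy condition |
| SAP 6.1.1, clinical question, and the sentence on what the estimand assesses | after Week 6 |
| SAP 6.1.1, Endpoint attribute | no start stated |
| SAP 6.1.1, treatment of interest | after Week 6 |
| SAP 6.1.1, event 1 and composite sentence | after Week 6 |
| SAP 6.1.3.1, scoring rule and data source | after Week 6 |
| Protocol 2.1 (question, treatment, event 1, composite sentence) and 12.4.3 | after Week 6 |

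One attribute lacks the start. Every text that says how to score a rescue user has it.

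**What the clause can mean.** The SAP does not formally define confounding therapy. The nearest text is the sentence on relevant medication, which rests on confounding potential. The protocol glossary (entry for Variable) allows the variable to state whether an intercurrent event occurred. The natural reading is therefore shorthand for the medication events, which carry their own timing in the list below it.

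**Whether early rescue can reach the flag.** For a different score, someone has to judge Weeks 1 to 6 rescue as confounding and pass that judgement to the programmer. The only visible adjudication is the blinded review in SAP 6.1.3.1, and its stated data are use after the first 6 weeks. No other visible step exists.

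**Size if the literal clause were applied.** Inputs from protocol 12.8.1: 32 on i.v. drug, 16 on pooled placebo, placebo rate 7%, difference 36 points. The i.v. rate is 0.07 + 0.36 = 0.43.

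- Expected responders: 16 × 0.07 = 1.12 on placebo and 32 × 0.43 = 13.76 on i.v. drug.
- One i.v. responder re-scored lowers the raw difference by 1/32 = 3.125 points. One placebo responder re-scored raises it by 1/16 = 6.25 points. Both are before the placebo prior is applied.
- Suppose a share r of would-be responders had confounding rescue in Weeks 1 to 6. The documents give no such rate, so r is an assumption.
  - Both groups, 0.36 × (1 − r): 36.0 points at r = 0, 32.4 at 10%, 25.2 at 30%.
  - Placebo only, 0.43 − 0.07 × (1 − r): 36.7 at 10%, 38.1 at 30%.
  - i.v. only, 0.43 × (1 − r) − 0.07: 31.7 at 10%, 23.1 at 30%.

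Under the visible scoring rule nobody is re-scored for early rescue, which is the r = 0 case. The stated 80% probability of success cannot be recomputed, because the decision criteria and the prior are blacked out. Nothing here depends on it.

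**Prohibited medication.** Event 2 has no window. In the treatment of interest the words for use are repeated before rescue, so the time limit attaches to rescue. Protocol 9.1.1.1 makes a participant who discontinues because of prohibited medication a non-responder, with no week limit. Table 6-2 calls for stopping study drug for most prohibited classes used during treatment; one row of topical agents is left to case-by-case discussion.

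**The case for a change.** The strongest case for a change is that an estimand should read one way in every attribute. Reading the clause through the sentence on relevant medication does not restore the Week 6 start, because that sentence has no time limit either. If SAP 6.1.3.1 governs, the Endpoint attribute taken literally is not what is analyzed. The blinded-review listing, as described, could not even supply what the literal clause would need. The repair is a few words, and with about one placebo responder expected, one re-scored participant is visible in the raw difference.

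The textual point stands: the clause omits a start that the surrounding text supplies, and tidier wording would read better. The step from there to a second analysis rule does not stand. An estimand is read across its attributes, and all the others agree on rescue. That the listing cannot feed the literal clause shows that the clause is not the working rule. The shifts of 1/32 and 1/16 are what any re-scored participant produces for any reason, so they say nothing about how often this clause would bite or in which direction.

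On prohibited medication, the data-source sentence in SAP 6.1.3.1 remains somewhat ambiguous. The event list, the treatment attribute and protocol 9.1.1.1 all point to a Week 6 limit on rescue only.

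**Conclusion.** No change follows. The Endpoint attribute is worded loosely, but the responder flag is settled by intercurrent events 1 to 4 and SAP 6.1.3.1, which give one Week 6 cut for rescue and match the protocol. An analyst working from these texts scores the early-rescue participant as a responder. Rewording the clause would tidy the page without altering a result: the expected number re-scored is zero under the visible rule, and the design difference stays at 36 points.

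This rests on two assumptions: that the blinded-review data cover the window that SAP 6.1.3.1 states, and that the blacked-out text after that sentence does not bring in earlier rescue. Nothing visible suggests otherwise, and the redaction cannot be held against the plan. The conclusion concerns only how the analysis flag is derived, not when rescue may be given.

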**Handling of remaining intercurrent events:**

1. Relevant use of rescue therapy (after first 6 weeks of treatment)
2. Relevant use of prohibited medication to treat AD symptoms or with impact on efficacy
3. Study treatment discontinuation due to lack of efficacy
4. Study treatment discontinuation due to AE related to AD, e.g. worsening of AD
5. Study treatment discontinuation due to AE not related to AD or due to lack of tolerability
6. Study treatment discontinuation due to other reasons (e.g. administrative if participant relocates to a region where the trial is not offered, or withdrawal of informed consent)

For the intercurrent events 1 to 4, a composite strategy will be used: use of any therapy (prohibited or rescue medication taken after the first 6 weeks) as well as any study treatment discontinuation due to lack of efficacy or due to AE related to AD are considered as unfavorable outcome, i.e. the participant will be treated as a non-responder.

For the intercurrent events 5 to 6, a treatment policy strategy will be used and the intercurrent event will be ignored (set data after discontinuation to be missing)

**The summary measure:** treatment difference of the CMK389 and placebo in absolute responder rates.

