## **2.1 Primary estimands**

The primary clinical question of interest is: What is the effect of the CMK389 treatment versus placebo on IGA response rate after 16 weeks of treatment in participants with moderate to severe AD without any relevant use of prohibited medication or use of rescue medication taken after the first 6 weeks.

Prohibited or rescue medication are relevant when their use may have a potential confounding effect on the efficacy assessment.

The justification for targeting this treatment effect is that we wish to estimate the effect of the study drug for the full duration when administered without any relevant use of prohibited medication or use of rescue medication taken after the 6 first weeks.

The primary estimand is described by the following attributes:

1. Population: Adult participants with moderate to severe AD is the target population for biologics ([Beck et al 2014](#), [Simpson et al 2016](#)) and is defined by an IGA score of moderate to severe (3 or 4) and an EASI score of at least 12. Further details about the population are provided in [Section 5](#).
2. Primary variable: IGA response (defined as clear or almost clear and at least 2 point reduction from baseline) at Week 16.
3. Treatment of interest: the randomized treatment (the investigational treatment CMK389 or the placebo treatment) taken for the entire study duration without any use of prohibited medications or use of rescue medication taken after the first 6 weeks.
4. The summary measure: Treatment difference of the CMK389 and placebo in absolute responder rates.

Handling of remaining intercurrent events:

1. Use of rescue therapy (after first 6 weeks of treatment)
2. Use of prohibited medication to treat AD symptoms or with impact on efficacy
3. Study treatment discontinuation due to lack of efficacy
4. Study treatment discontinuation due to AE related to AD, e.g. worsening of AD
5. Study treatment discontinuation due to AE not related to AD or due to lack of tolerability
6. Study treatment discontinuation due to other reasons (e.g. administrative if participant relocates to a region where the trial is not offered, or withdrawal of informed consent)

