For the intercurrent events 1 to 4, a composite strategy will be used: use of any therapy (prohibited or rescue medication taken after the first 6 weeks) as well as any study treatment discontinuation due to lack of efficacy or due to AE related to AD are considered as unfavorable outcome, i.e. the participant will be treated as a non-responder.

For the intercurrent events 5 to 6, a treatment policy strategy will be used and the intercurrent event will be ignored.

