Participants who discontinue study treatment or who decide they do not wish to participate in the study further should NOT be considered withdrawn from the study UNLESS they withdraw their consent (see [Section 9.1.2](#) 'Withdrawal of Informed Consent' section). Where possible, they should return for the assessments indicated in the Assessment Schedule in [Section 8](#). If they fail to return for these assessments for unknown reasons, every effort (e.g. telephone, e-mail, letter) should be made to contact the participant/pre-designated contact as specified in the lost to follow-up section ([Section 9.1.3](#)). This contact should preferably be done according to the study visit schedule.

If the participant cannot or is unwilling to attend any visit(s), the site staff should maintain regular telephone contact with the participant, or with a person pre-designated by the participant. This telephone contact should preferably be done according to the study visit schedule.

After study treatment discontinuation, at a minimum, in abbreviated visits, the following data should be collected at clinic visits or via telephone/email contact:

- New / concomitant treatments
- Adverse Events / Serious Adverse Events

The investigator must also contact the NIRT to register the participant's discontinuation from study treatment.

If discontinuation occurs because treatment code has been broken, please refer to Emergency breaking of treatment code [Section 6.6.3](#).

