#### **9.1.1.1 Replacement policy**

Participants may be replaced until the study has 64 total evaluable participants. The evaliability of the participant will be defined by availability of baseline data and suitable EoT visit data as well as the administration of at least 3 out of 4 doses of the study drug. If any patient discontinues treatment because of prohibited medication (refer to [Section 6.2.2](#)), the patient will not be replaced and will be considered as a non-responder for the primary analysis.

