#### **9.1.2 Withdrawal of informed consent**

Participants may voluntarily withdraw consent to participate in the study for any reason at any time. Withdrawal of consent occurs only when a participant:

- Does not want to participate in the study anymore,  
and
- Does not want any further visits or assessments  
and
- Does not want any further study related contacts

In this situation, the investigator should make a reasonable effort (e.g. telephone, e-mail, letter) to understand the primary reason for the participant's decision to withdraw his/her consent and record this information.

Where consent to the use of personal and coded data is not required, the participant cannot withdraw consent. They still retain the right to object to the further use of personal data.

Study treatment must be discontinued and no further assessments conducted, and the data that would have been collected at subsequent visits will be considered missing.

Further attempts to contact the participant are not allowed unless safety findings require communicating or follow-up.

All efforts should be made to complete the assessments prior to study discontinuation. A final evaluation at the time of the participant's study discontinuation should be made as detailed in the assessment table in [Section 8](#).

Novartis will continue to retain and use all research results (data) that have already been collected for the study evaluation.

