#### **12.4.3 Handling of remaining intercurrent events of primary estimand**

Use of any therapy (prohibited or rescue medication taken after the first 6 weeks) as well as any study treatment discontinuation due to lack of efficacy or due to an AE related to AD are considered as unfavorable outcomes, and therefore the participants will be treated as non-responders (composite strategy). Study treatment discontinuation due to other reasons and AEs not related to AD or due to lack of tolerability will be handled with a treatment policy strategy (i.e. they will be ignored).

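### SAP 6.1.1 labels the handling of intercurrent events 5 and 6 as treatment policy but sets data after discontinuation to missing, contradicting that label and the protocol's primary estimand

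*SAP*

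**What the plan says.** The protocol lists six intercurrent events for the primary estimand. Events 1 to 4 (late rescue, prohibited medication, stopping for lack of efficacy, stopping for an AD-related adverse event) make the participant a non-responder. Event 5 is stopping for an adverse event unrelated to AD or for poor tolerability. Event 6 is stopping for other reasons, including relocation and withdrawal of consent.

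- Protocol 2.1: "For the intercurrent events 5 to 6, a treatment policy strategy will be used and the intercurrent event will be ignored".
- Protocol 12.4.3: these discontinuations "will be handled with a treatment policy strategy (i.e. they will be ignored").
- SAP 6.1.1, handling of remaining intercurrent events: a "treatment policy strategy will be used and the intercurrent event will be ignored (set data after discontinuation to be missing").
- SAP 6.1.3.1 again says treatment policy and ignored, adds that nothing needs to be carried forward, and has no step that sets data to missing.
- SAP 6.1.3.2 plans no imputation for the primary endpoint.

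On data collection, Protocol 9.1.1 keeps participants who stop treatment in the study unless they withdraw consent, and says: "Where possible, they should return for the assessments indicated in the Assessment Schedule". After withdrawal of consent, Protocol 9.1.2 says that "the data that would have been collected at subsequent visits will be considered missing".

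**The concern.** A treatment policy strategy takes the outcome as observed, whatever happened to treatment. An instruction to set data after discontinuation to missing does the opposite: it lets the discontinuation decide which outcomes count. It moves the analysis towards an on-treatment question, which the protocol does not assign to events 5 and 6. The SAP states that it implements the analysis planned in the protocol, but on this point it changes it.

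This is the only primary endpoint of a proof-of-concept study meant to inform further development. If even one participant with event 5 or 6, and none of events 1 to 4, has an observed Week 16 IGA, the protocol rule uses that value and the SAP rule discards it. The resulting estimate does not then target the stated estimand. Leaving two readings open until after unblinding would also allow the choice between them to depend on the results.

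**Working it through.** **Step 1: the texts side by side.** Protocol 2.1, Protocol 12.4.3 and SAP 6.1.3.1 all say treatment policy and ignored. Only SAP 6.1.1 adds deletion. SAP 6.1.3.1 should be aligned, but its silence on deletion is not in itself a clear contradiction of 6.1.1.

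**Step 2: can affected values exist?** Yes, but not for everyone. Protocol 9.1.1 seeks scheduled assessments after stopping. However, its minimum data set for abbreviated visits covers only new or concomitant treatments and adverse events, not IGA. After consent withdrawal the value is missing under either rule.

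**Step 3: what happens to a deleted value?** SAP 6.1.3.2 plans no imputation, and its heading concerns values unrelated to an intercurrent event. No visible rule therefore fills the gap, and the participant most likely leaves the responder-rate denominator. This is an inference, because the model text is redacted.

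**Step 4: the plan's own figure.** Protocol 12.8.1 gives an 80% probability of meeting the dual criteria. The thresholds and the MAP prior are not public, so this cannot be properly reproduced. The point does not depend on it.

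**Step 5: effect of one deleted IGA (illustration).** Inputs from Protocol 12.8.1: 32 on CMK389 i.v., 16 on pooled placebo, placebo rate 7%, difference 36 points, hence active rate 7% + 36 = 43%. Assumptions: retained participants respond at these rates; simple proportions; no MAP prior.

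In an arm of size n with retained rate r, one participant with event 5 or 6 has outcome y (1 = responder, 0 = not). The SAP rule gives r. The protocol rule gives [(n - 1)r + y]/n. SAP minus protocol is (r - y)/n in that arm, and the sign reverses for placebo when the treatment difference is taken.

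- Active non-responder: 0.43/32 = +1.3 points.
- Active responder: (0.43 - 1)/32 = -1.8 points.
- Placebo non-responder: -(0.07/16) = -0.4 points.
- Placebo responder: -(0.07 - 1)/16 = +5.8 points.

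**Step 6: a larger scenario (assumed).** A share d of the active arm has a deleted IGA and would respond at 7%; placebo discontinuers respond like retained placebo participants. The active rate under the protocol rule is (1 - d) x 0.43 + d x 0.07.

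- d = 10%: 0.387 + 0.007 = 39.4%; difference 39.4 - 7 = 32.4 points.
- d = 20%: 0.344 + 0.014 = 35.8%; difference 35.8 - 7 = 28.8 points.
- SAP rule in both cases: 43 - 7 = 36 points.

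If discontinuers in both arms respond like retained participants, the two rules agree and the shift is zero.

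**The case against.** **The parenthesis may only describe absent data.** Event 6 includes consent withdrawal, after which nothing is collected, and SAP 6.1.3.1 says that no carrying forward is needed. The author may have meant only that absent values stay absent. But the sentence is an instruction covering all discontinuations under events 5 and 6, which is wider than consent withdrawal. At the least it needs clarifying.

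**The label, not the parenthesis, may be the error.** The protocol defines the treatment of interest as "the randomized treatment (the investigational treatment CMK389 or the placebo treatment) taken for the entire study duration", and the SAP as that "actually taken for the entire study duration without any use of prohibited medications". Both sit badly with treatment policy for discontinuation. This objection stands in part: the documents do not settle which half was intended. Either way, the text must change.

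**The practical effect may be small.** An affected participant must stop for event 5 or 6, remain in follow-up, have a Week 16 IGA, and have none of events 1 to 4. The documents give no rate for this. A share of 10% to 20% of 32 means 3.2 to 6.4 people, and nothing in the documents supports that many. The +5.8 figure needs a placebo responder, at a planning rate of 7%, and the MAP prior would normally dampen a single placebo result. The study is also described as non-confirmatory. All of this limits what can be said about size; none of it reconciles the sentence with its label.

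**The replacement policy.** A reader might infer from Protocol 9.1.1.1 that someone who stops after the third dose is sure to have a Week 16 IGA. Evaluability there means "availability of baseline data and suitable EoT visit data as well as the administration of at least 3 out of 4 doses", but this governs replacement, not the primary analysis. The visit schedule is redacted, so an end-of-treatment visit after early stopping cannot be equated with Week 16.

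**Conclusion.** The contradiction is certain on the visible text, and no redacted model could turn deletion of post-event data into treatment policy. It should be corrected before unblinding because it concerns the primary estimand.

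The numerical effect is not established. It rests on an inferred denominator, unknown counts and unknown off-treatment responses. A reader might infer that the SAP rule inflates the planned 36 points by 3.6 to 7.2. The illustration does not show that: there the SAP rule returns 36 and the protocol rule returns 32.4 to 28.8, on an assumed discontinuation share. A reader might also infer that the rule favours CMK389. The one-participant shifts run in both directions, so the documents do not support that either.

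**What to change.** In SAP 6.1.1, delete the parenthesis that sets data after discontinuation to missing. State that every observed Week 16 IGA is used regardless of events 5 and 6, unless one of events 1 to 4 makes the participant a non-responder. Align SAP 6.1.1, 6.1.3.1 and 6.1.3.2 with Protocol 2.1 and 12.4.3, and state the denominator when a Week 16 IGA is truly missing, for example after consent withdrawal. Reconcile the treatment-of-interest wording in both documents with the strategy chosen.

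If the sponsor does intend to exclude off-treatment data, the alternative is to stop calling it treatment policy, and to rename and justify the strategy in both the protocol and the SAP.

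The cost is a few sentences. A sensitivity analysis counting truly missing values as non-responders would add one table; it is optional and not needed to cure the contradiction. The estimate may move in either direction, or not at all.
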